## Exploratory Analysis

Additional analyses can be conducted after the trial is completed that are not specified in the trial protocol. However, it is useful to specify areas of potential future interest here.

Regression models will be used to explore compliance with the treatment status, using binary logistic regression to predict:

- Any gains in YP CORE scores based on types of treatment (group therapy, 1-21 session)
- Dose response, i.e. including a measure of the number/proportion of sessions into the regression model to explore effect on YP CORE growth (baseline versus outcome)
- Sociodemographics – A suite of socio-demographic and other variables, collected from the administrative data, will be included into the impact regression models to test for differences in the YP CORE. These include:
  - Age
  - Gender
  - Country of origin
  - Length of time in UK
  - Relationship status
- Where feasible, i.e. group sample sizes permitting, selected interaction terms will subsequently be investigated to provide exploratory hypotheses for further research.

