## Design

Table 3: RCT design details

|   |                                |  |
|---|--------------------------------|--|
| Trial type and number of arms            |                                | Non-blinded parallel two-armed randomised control trial with UASC individually randomised to a treatment or waitlist control group (on rolling basis)  |
| Unit of randomisation                    |                                | Young person   |
| Stratification variables (if applicable) |                                | Overall, 6 strata will be used, comprising of one high-risk stratum and five moderate risk strata defined by the British Refugee Council locations, which include four with physical geographical boundaries and a fifth with virtual boundaries. Allocation rates are 50 : 50 for UASCs in moderate risk strata and 66: 34 in high risk strata. |
| Primary outcome                          | Variable                       | Continuous variable – scores ranging from 0 to 40  |
|   | Measure (instrument, scale)    | Mean intervention group YP-CORE score compared to mean control group YP-CORE score collected at endline (3 months from start of intervention) by delivery staff i.e. therapists  |
| Secondary outcome(s)                     | Variable(s)                    | Continuous variable – scores ranging from 7 to 35  |
|   | Measure(s) (instrument, scale) | Mean intervention group SWEMWBS score compared to mean control group SWEMWBS score collected at endline (3 months from start of intervention) by delivery staff i.e. therapists  |

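### The exploratory section places a continuous 0–40 score under binary logistic regression, and none of its listed outcomes is the compliance that the model is said to explore

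*Protocol*

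**What the plan says.** The Exploratory Analysis section of the protocol opens its list with one sentence that sets both purpose and model: regression is to explore compliance, "using binary logistic regression to predict" what is listed beneath. Three substantive items follow.

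- Therapy type: "Any gains in YP CORE scores based on types of treatment" (group or one to one).
- Dose response: "including a measure of the number/proportion of sessions into the regression model to explore effect on YP CORE growth (baseline versus outcome".
- Sociodemographics: age, gender, country of origin and similar variables "will be included into the impact regression models to test for differences in the YP CORE".

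A last item leaves room for selected interaction terms.

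Elsewhere the protocol treats the score differently. Table 3 in the Design section defines the primary outcome as "Continuous variable – scores ranging from 0 to 40". The Primary Analysis section fits ordinary least squares with baseline YP-CORE and stratum indicators (equation 1), and gives the continuous nature of the score as a reason. The Outcome Measures section describes YP-CORE as a measure of psychological distress, so a lower score is better.

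**The concern.** Purpose, model and outcomes do not match. The purpose is compliance, yet no item has compliance as its outcome, although the protocol has binary measures that would serve: receipt of treatment in equations (2) and (3), and the share reaching the treated threshold in Table 5.

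The model is binary, yet only the therapy-type item is worded as a yes/no outcome. That wording counts a 1-point and a 15-point change alike. The dose-response item describes growth from baseline to endline, which a binary logistic model cannot take without a cut-point, and none is given. The sociodemographic item sits under the logistic lead-in but names the impact models, which are linear.

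Direction is also open. Read plainly, a gain in score on this instrument means more distress. The risk of miscoding is real: the Sample Size section illustrates its detectable effect as a treated mean of 20.1 or above against a control mean of 18.3, which on this scale is a worse result.

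At stake are precision in comparisons that are already small, and comparability: an odds ratio for any gain cannot be set beside the primary mean difference in points.

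**Working it through.** **1. The protocol's own figure.** No power or precision is stated for the exploratory analyses. The only stated figure is the primary MDES of 0.24 (Table 4: 145 and 135 cases, R² = 0.5, power 0.8, two-sided alpha 0.05). With P = 145/280 = 0.518:

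MDES = (1.96 + 0.84) × √[(1 − 0.5) / (0.518 × 0.482 × 280)] = 0.237, or 0.238 with t quantiles. The stated figure reproduces, and nothing below changes it.

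**2. Information kept after dichotomising.** For a normal variable cut so that a share p improves, efficiency relative to the same variable kept continuous is φ(z_p)² / [p(1 − p)]. The protocol gives no p, so a range is shown.

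| Share improving (assumed) | Efficiency | Loss | 280 cases worth about |
|---|---|---|---|
| 50% | 0.637 | 36% | 178 |
| 60% | 0.622 | 38% | 174 |
| 70% | 0.576 | 42% | 161 |
| 80% | 0.490 | 51% | 137 |

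The 36% at p = 0.5 is 1 − 2/π, the smallest loss possible under normality.

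**3. Against the baseline-adjusted linear model.** A change score is itself less efficient than adjusting for baseline. With the protocol's pre-post correlation of 0.71, its relative efficiency is (1 − 0.71²) / [2(1 − 0.71)] = 0.855. A dichotomised change score without baseline therefore keeps 0.855 × 0.637 = 0.544 at p = 0.5, a loss of about 46%.

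A simulation checks this: 2,000 runs per row, 145 against 135 cases, the SD of 7.6 and mean of 18.3 that the protocol uses for illustration, correlation 0.71, effect 0.24 SD, scores rounded and limited to 0–40. It uses a two-group contrast to measure relative efficiency and does not model the therapy-type comparison itself. The protocol does not say whether baseline enters the logistic model, so both versions are shown.

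| Controls improving (assumed) | Power, linear | Power, logistic (without / with baseline) | Loss |
|---|---|---|---|
| 46% | 0.80 | 0.57 / 0.61 | 46% / 41% |
| 66% | 0.80 | 0.48 / 0.52 | 53% / 48% |
| 78% | 0.80 | 0.40 / 0.45 | 63% / 60% |

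**4. Therapy type.** The Summary expects about 190 one-to-one and 57 group participants. Assume that mix holds among the 123.5 moderate-risk treatment cases: 123.5 × 190/247 = 95 and 123.5 × 57/247 = 28.5. The detectable difference with the continuous score is 2.80 × √[0.5 × (1/95 + 1/28.5)] = 0.42 SD. Dividing by the square root of the efficiency in step 2 gives 0.53 SD (50% improving) or 0.56 SD (70%). Using the 0.544 of step 3 instead gives 0.42/√0.544 = 0.57 SD.

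**5. Dose response, if a cut at zero were imposed.** Assume 145 treated cases with full follow-up and correlation 0.71. For an assumed standardised dose effect of −0.17, simulated power is 0.81 linear, against 0.54 (without baseline) and 0.57 (with baseline) logistic. For −0.10 it is 0.39 against 0.22 and 0.24. Under the null all rejection rates are 0.04–0.05. Converting power to information by 1 − [(1.96 + z_logistic)/(1.96 + z_linear)]², where z is the normal quantile of the power, gives a loss of 43–47% for the larger effect and 44–50% for the smaller.

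**The case against.** The strongest reply is that this is loose drafting in a section of possible future interest. No sample size or confirmatory claim rests on it, and the exact models for exploratory work are commonly left to a statistical analysis plan, which is not shown. That stands as to weight. It does not remove the point, because the section names a model and the named model does not fit the outcomes listed beneath it.

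A reader might infer more than the protocol supports:

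- **That every exploratory analysis is a logistic model of any gain.** Only the therapy-type item is worded so. For dose response the fault is a mismatch between model and outcome, and the sociodemographic item points to the linear models, so the loss need not apply there.
- **That this is the only look at number of sessions.** The ethics section on outcomes getting worse before they improve also plans, if data allow, to examine trends in outcomes by sessions attended. It names no model and no dichotomy.
- **That the linear model is used everywhere else.** The Sensitivity Analysis section allows an ordinal model if the secondary outcome is skewed.
- **That the loss is a fixed third.** About 36% is the best case, and the actual figure depends on a share improving that the protocol does not give.

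It is also fair to say that a responder summary can help readers. That supports reporting one descriptively, with a stated threshold, rather than as the model for type and dose.

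**Conclusion.** The point holds as an internal inconsistency with a better method available at no cost. The lead-in promises a compliance analysis that the list does not contain. It prescribes a binary model for one item that discards information and for another that the model cannot fit as described. It also leaves the direction of gain undefined.

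The loss from dichotomising is at least about 36% under normality, and about 41–63% against baseline-adjusted least squares in the scenarios simulated. These figures rest on assumed shares improving, assumed effect sizes, normal scores and full follow-up. The Missing Data section plans a complete-case analysis, so the numbers available would probably be smaller.

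Severity is low. The primary and secondary estimates, the MDES and the sample size are untouched.

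**What to change.** Reword the Exploratory Analysis section as follows.

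1. For therapy type and for number or proportion of sessions, use linear regression of endline YP-CORE on that variable, adjusted for baseline YP-CORE and stratum, in the form of equation (1).
2. Keep logistic regression for a binary compliance outcome, and say which one: receipt of treatment, or reaching the treated threshold in Table 5.
3. State that the sociodemographic variables enter the linear impact models, and take that item out from under the logistic lead-in.
4. Define improvement as a lower YP-CORE score.
5. Describe the type and dose coefficients as non-randomised associations, since neither therapy type nor attendance is randomly assigned.

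The cost is a change of wording. The same data and software serve, and the sample size does not change.

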## Contextual Factors Analysis

A key contextual factor in this trial is the nature of treatment delivery virtually and in the four authorities. Administrative data will be available on the flow process of UASCs referred for treatment and these numbers will be compared across the different treatment centres alongside caseload, levels of engagement of the young people and so forth. The analysis will include basic descriptive statistics of the administrative data accompanied by evidence from interviews undertaken in the process evaluation.

# Implementation and Process Evaluation

## Aims

The implementation and process evaluation (IPE) aims both to answer distinct IPE questions and to create understanding around implementation outcomes that are useful for complementing and understanding the findings from the RCT impact evaluation. This knowledge is important for understanding the programme, its implementation in this evaluation, and creating knowledge for a potential scale up of the programme. As such, the key research questions addressed by the IPE will focus on the implementation outcomes that are a precursor to positive intervention effects and appropriate to understanding 'My View' intervention which is still developing and being refined. These research questions build upon the pilot evaluation published by the British Refugee Council, for example by looking at the appropriateness and fit of the programme, acceptability, and cultural barriers to engagement. At the same time, the research questions also acknowledge the importance of revisiting and specifying the current intervention further, including understanding the mechanisms for change, specifying the intervention activities that have taken place, and examining new elements such as the online delivery.

Critical in the IPE data collection activities will be the understanding of the context of mental health for UASC and the context of delivery for partners. Although we are specifying our plans here, we will be flexible to the needs of delivery of the intervention and the needs of the populations served by the intervention, and we may modify sample sizes and data collection activities accordingly (e.g., for example, by allowing flexibility in the interview and bringing in more arts-based methods rather than semi-structured interviews or by not recruiting young people with particularly vulnerable mental health at the end of the intervention).

## Logic Model development

An important component of both the RCT and IPE is specifying the logic model (LM). WWCS facilitated an initial LM workshop at the launch and this was followed up with several other workshops and revisions led by the evaluation team. The logic model development focus on identifying the key target activities, implementation outcomes, mechanisms of change, outcomes, and assumptions. We will subsequently refine the LM in the light of study data.

## Research Questions

We have grouped key IPE questions around Proctor et al. (2011)'s conceptual model that categorises implementation outcomes and distinguishes these from service and individual outcomes. The data collection proposed is shown alongside these in the table and described further in the design section.

Research questions:

1. **Mechanisms of change:** What are the perceived mechanisms of change for 'My View' to intended outcomes for young people? What are the perceived changes in outcomes?
2. **Adoption:** What is the programme reach? How many took up the service? What kinds of activities did they do, and what referrals were made and followed upon?
3. **Acceptability:** How acceptable do participants and staff find 'My View' (e.g., content, comfort, number of sessions, online nature)? Is it viewed as an improvement on services as usual by young people, delivery partners, and social workers? What adaptations have been made to make the programme more acceptable and culturally acceptable to participants?

---

4. **Appropriateness:** Is 'My View' seen as a good fit with professional/service norms (e.g. counselling co-location, therapy, psychoeducational services) and with needs of UASC (e.g. addressing mechanisms for change)?
5. **Feasibility:** What are viewpoints on the feasibility of implementing 'My View'? What barriers and enablers were encountered, and how were these addressed?
6. **Implementation strategies:** What implementation strategies were used to recruit UASC, establish the service, and train / support 'My View' staff?

## Design

Table 5 below provides an overview of the indicator, output, or frame of analysis for each research question and how we intend to collect this data.

Table 5: IPE design table

| IPE Design Table  |  |
|---|--|
| Indicators, output, or analysis   | Method   |
| 1. Mechanisms of change: What are the perceived mechanisms of change for 'My View' to achieve the intended outcomes for young people?  |  |
| 
 
● Logic model diagram
 
● Perceived changes in service and client outcomes including unintended consequences and risks of harm               
 
○ Perceived changes in services and access to services (e.g. access to education and housing, timeliness in services)
 
○ Perceived impacts on young people (e.g., symptomatology, negative peer influences)
 
 
 
  | 
 
● Logic model workshops
 
● Interviews with staff
 
● Interviews with young people
 
 |
| 2. Adoption: What is the programme reach? How many took up the service? What kinds of activities did they do, and what referrals were made and followed upon?  |  |
| 
 
● Number of referrals
 
● Number of eligible referrals
 
● Numbers taking up               
 
○ One-to-one therapy
 
○ Group therapy
 
 
 
● Number of sessions completed within the 12 weeks 'treatment period'               
 
○ Mean, median, mode
 
○ Percentage reaching threshold of 'treated'
 
 
 
● Description of services and activities undertaken
 
● Number of young people who were overridden allocation from the RCT
 
● Justifications for overriding RCT allocation
 
● Number and types of onwards referrals made               
 
○ Any data on referrals accepted
 
 
 
 | 
 
● Individual-level administrative data – Records by the British Refugee Council
 
                  |
| 3. Acceptability: How acceptable do participants and staff find 'My View' (e.g., content, comfort, number of sessions, online nature)? Is it viewed as an improvement on services as usual by young people, delivery partners, and social workers? What adaptations have   |  |

**been made to make the programme more acceptable and culturally acceptable to participants?**

- |   |   |
|---|---|
| 
 
● Perceived acceptability
 
● Perception of cultural acceptability
 
 | 
 
● Interviews with children and young people
 
● Interviews with staff members, including therapeutically-trained interpreters
 
● Interviews with stakeholders (e.g., KRAN, other refugee-serving organisations, CAMHS, foster carers, accommodation workers)
 
 |
|---|---|

**4. Appropriateness: Is 'My View' seen as a good fit with professional/service norms (e.g. counselling co-location, therapy, psychoeducational services) and with needs of UASC (e.g. addressing mechanisms for change)?**

- |   |  |
|---|--|
| 
 
● Perceived appropriateness
 
 | 
 
● Interviews with children and young people
 
● Interviews with 'My View' staff members
 
● Interviews with stakeholders
 
 |
|---|--|

**5. Feasibility: What are viewpoints on the feasibility of implementing 'My View'? What barriers and enablers were encountered, and how were these addressed?**

- |  |  |
|--|--|
| 
 
● Perceived feasibility
 
● Perceived barriers and enablers
 
● Perceived strategies for overcoming barriers and facilitating enablers
 
 | 
 
● Interviews with 'My View' key staff members
 
● Interviews with intervention trainers and facilitators
 
● Administrative data on implementation
 
 |
|--|--|

**6. Implementation strategies: What implementation strategies were used to recruit UASC, establish the service, and train / support 'My View' staff?**

Implementation strategies classified using the Expert Recommendations for Implementing Change (ERIC) compilation of 73 commonly identified and clearly defined implementation strategies in human services. We will pay particular attention to the implementation strategies around engaging young people, adapting and tailoring to context, and supporting clinicians.

- Interviews with 'My View' Workers
- Analysis of documents about the programme
- Administrative data on workshops and recruitment

## Methods

### Sample and Recruitment

Administrative data will be pseudonymised individual-level data and aim to comprehensively cover all referrals and participants and will be shared with appropriate data protection safeguards, data protection impact assessments, and using data sharing agreements.

Interview participants will be purposively sampled across the four geographic sites and remote delivery per the target numbers below under data collection. We will recruit by providing information sheets through the British Refugee Council for interviews via an opt-in basis. We will provide information on the evaluation in the training for British Refugee Council and provide support for recruitment throughout the evaluation. For adult stakeholders, we may also recruit through networks and publicly available contact information.

Interviews with children and young people after completion of the programme, so as not to interfere with counselling or intervention outcomes (n=40), with purposive sampling across the 4 sites and amongst participants who completed the 1:1 session, who did group sessions, who had crisis support, and a few who were offered the programme but decided not to participate. The exact sampling frame will be decided in consultation with the programme when distribution of participants and their demographics are better understood. We will not aim for a representative sample, but we will aim to sample purposively for a diversity of experiences and information, while ensuring that participation is entirely voluntary and that there is understanding in order to be able to consent to participation. Information sheets and consent forms will be translated into appropriate languages. We plan to compensate participants £20 for 1-hour of their time for interviews and to provide interpreters and translation of information and consent sheets where appropriate.

## Data Collection

Administrative data collection will build off the British Refugee Council's extensive existing data collection systems.

We will use semi-structured interview guides for all interviews. We anticipate that most, if not all, of the interviews will take place over the phone and or video conference (per the preference of the interviewee).

Data collection will take place with the target sample sizes and time points in the data collection schedule (Table 6) below.

*Table 6: IPE data collection schedule*

| Method  | Sample size  | Time point                           |
|---|--|--------------------------------------|
| Administrative data   | All referrals and participants                                   | June 2021-April 2022                 |
| Semi-structured interviews with children and young people after completion of the programme                                       | 40 children and young people                                     | Nov 2021-April 2022                  |
| Semi-structured interviews with key therapists and staff  | 6-8 therapists and key staff at 2 time points (12-16 interviews) | July-August 2021
March-April 2022 |
| Semi-structured interviews with other staff such as intervention trainers, facilitators, and therapeutically-trained interpreters | 4-6 interviews   | Feb-March 2022                       |
| Semi-structured interviews with stakeholders in each location   | 20 interviews with stakeholders (5x4 locations)                  | Feb-March 2022                       |

## Analysis

All interviews will be transcribed. Qualitative analysis will begin by using coding by using a platform for data management and coding. The coding framework will be developed both deductively (e.g., reflecting elements of the questions, and logic model) and inductively, including unexpected issues emerging in the data. This will be an iterative process with multiple researchers to ensure the quality of coding structures. A framework analysis will be used to chart

 We are still confirming whether we will use dedoose or NVivo. In the application stage, dedoose appeared to offer the best value for money, but we are confirming this.

at the key themes across the four sites as cases of implementation, thereby examining trends in findings between and across categories of interviewees and locations.

To ensure implementation strategies are uniformly classified across the four sites, we will classify them using the Expert Recommendations for Implementing Change (ERIC) compilation of 73 commonly identified and clearly defined implementation strategies in human services. We will pay particular attention to the implementation strategies around engaging young people, adapting and tailoring to context, and supporting clinicians. Understanding implementation strategies is core to understanding the results of the RCT as well as for replication and improvement of 'My View.'

---

